### ***4.4 Variables***

#### **4.4.1 Efficacy, acceptability:**

- Difference in the proportion of women who successfully have the IUC inserted (success versus failure),
- Continued use of IUC at 3 and 12 months post insertion evaluated by telephone/email follow-up (continued use/voluntary discontinued use, involuntary discontinued use including expulsions etc) reasons for discontinuation will be recorded and subsequent use of other contraceptive methods will be noted)
- Ease of insertion according to health care provider (judged as very easy, easy, moderately, or very difficult)
- pain at time of insertion (women will indicate the pain before insertion, at placement of tenaculum, sound and IUC by putting a vertical mark on a 10 cm long horizontal line with

a Visual Analogue Scale (VAS) from 0, indicating no pain to 10 indicating worst imaginable pain. Result will be noted in millimeters and entered into case report forms).

- Post-abortion bleeding (number of days of fresh bleeding and spotting after the abortion)
- Reasons for non-attempted insertion of IUC (change of mind, heavy bleeding, not coming for insertion, staff being unavailable etc),
- Pregnancies occurring during the 12 month follow-up (planned and unplanned, wanted and unwanted, pregnancy outcomes- ectopic, miscarriage, abortion, molar, kept pregnancy),
- Acceptability of immediate and delayed insertion of IUC by asking women if they would recommend the procedure to a friend (yes/no, asked at the time of insertion and at the 3, 6 and 12 month follow up),
- Acceptability of IUC as post abortion contraception- evaluated as above,

[figure not shown]
#### **4.4.2 Safety:**

- Expulsion rate during 12 months following insertion in both groups evaluated by telephone follow up at 3, 6 and 12 months post abortion (complete, partial or no expulsion. The exact day of expulsion will be noted to determine the risk of expulsion as a function of time post insertion),
- Complications (adverse events (AE) and serious AE) bleeding requiring any treatment, uterine perforations and cervical tears, infection requiring treatment with antibiotics, hospitalization for any reason, surgical procedures due to heavy bleeding, incomplete abortions, prolonged bleeding or patient request,
- The proportion of surgical procedures in total and for each study site (type of procedure, reasons therefore- infection, retained products of conception, prolonged bleeding etc).

## **5 Design**

The study protocol is designed as a superiority trial according to the recommendations in the CONSORT statement for randomized superiority trials ([www.consort-statement.org](http://www.consort-statement.org)). It is defined as a Phase III trial (therapeutic confirming).

The flow of patients is presented in this flowchart.

**Research questions:**

- Does immediate post placental insertion of IUC result in higher use of IUC at 6 months post medical abortion compared to delayed insertion at 2-4 weeks post abortion?
- Can immediate insertion be performed with maintained safety and acceptability of IUC insertion?
- Which factors determine use of IUC after medical abortion?

This multicenter trial will investigate IUC use, safety and acceptability of immediate insertion of IUC within 0-48 hours after a completed medical abortion compared with delayed (routine) insertion at 2-4 weeks post abortion, which is current practice in women having medical abortion at a pregnancy length up to and including 21+6 days (as this is the current practice for judging healthy fetuses as viable outside the uterus) and opting for IUC for post abortion contraception. We will stratify the women in three gestational age categories ( $\leq 9$  weeks+0 days, 9weeks +1 day  $\leq 12$  weeks+0 days, and  $>12$  weeks) to make study data more internationally applicable as medical abortion in some countries is only used for early ( $<9$  weeks gestation) or second trimester abortions.

**Sample size and calculated power**

*Justification of power calculation*

A total of 720 women will be recruited. In order to be able to show a difference of 80 percent in IUC usage in the immediate insertion group at 6 months post insertion compared to 60 percent use in the delayed group with a power of 90 percent and an alpha of 0.05 we would need to randomize 109 women in each group.

If close to 100 percent of women receive the IUC in the immediate group and there is an expulsion rate of maximum 15 percent (immediate post placental insertion after delivery has expulsion rates of 15 percent) and some women have the IUC removed a use of approximately 80 percent could be expected in the immediate group. In the delayed group fewer women are estimated to come for insertion and the expulsion rate is estimated at 5 percent.

We will stratify women in three gestational age categories ( $\leq 9$  weeks+0 days, 9weeks +1 day  $\leq 12$  weeks+0 days, and  $>12$  weeks) to make study data more internationally applicable. We will compensate for surgical procedures due to incomplete abortions and prolonged bleeding which is estimated to be needed in approximately 3-5 percent (13). We will also compensate for a 15 percent loss to follow up which is commonly seen in studies in abortion. Thus, we will randomize 240 women in each gestational strata (total 720 women). Analysis will be presented as intention to treat for all randomized women as well as per protocol for women completing the 6 month follow up (see analysis plan). Follow up at 3, 6 and 12 months will be performed by telephone/email. In women who do not attend FU electronic patient records will be searched for main and secondary outcomes (safety, pregnancy, abortion).

Women will be recruited at several sites in Sweden. Recruitment (numbers) is not expected to be equal at each site but this will be considered in the statistical analysis.

Statistical advice from statistician [name] (adjunct professor and professional medical statistician) has been sought for study design, power calculation, and analysis plan.

Randomization:

The randomization ratio between intervention and control group will be 1:1 in permuted blocks of 4-8 in three strata and per site.

Randomization will be performed by the midwife in the family planning/ abortion clinic at the time of intake of mifepristone after the patient has been judged eligible for participation and has signed informed consent in the presence of the attending physician. Allocation to intervention or control will be performed via opening of opaque sealed envelopes in consecutive order. Each site will have a separate randomization sequence. All women will be identified through a patient log with name and Swedish personal identification number and the randomization number. The randomization number will be used on all paper and eCRFs. The study will for practical and ethical reasons not be blinded. The medical abortion will be performed according to the Swedish national guidelines.

Choice of study design:

The project will be performed as a randomized, controlled, multicenter superiority trial. It is known that sociodemographic factors such as parity and age may influence the choice of contraception and the rate of continued use. The rate of expulsion may be influenced by parity and gestational length. To eliminate these confounders the randomized design is superior. Many of the factors studied such as the primary outcome are objective and should not be affected by the non-blinded design. It is not deemed feasible to do a single blinded study where the health care provider would be blinded to the insertion time as the women with immediate insertion will likely be bleeding more than the women with delayed insertion. The women with immediate insertion will also have an open outer cervical os. Therefore, the health care provider would likely be affected by these findings at the IUC insertion.

**Primary outcome** will be the use of IUC at 6 months follow up. A difference of 20 percent between the study groups (immediate versus delayed insertion) will be considered as clinically significant (please see justification for power calculation).

**Secondary outcomes** include the rate of IUC inserted, rate of expulsion, pain at insertion, bleeding, reasons for non-insertion of IUC, IUC use, complications, acceptability, pregnancies and abortions evaluated at 3 and 6 months follow up and annually up to five years.

### **Variables and measures**

Primary outcome measure:

- Use of IUC at 6 months post insertion evaluated by telephone follow-up and through patient records. This will be evaluated as the proportion of women in each gestational strata (use of IUC versus no use of IUC).

Secondary outcome measures:

- Difference in the proportion of women who successfully have the IUC inserted (success versus failure),
- Expulsion rate during 12 months following insertion in both groups evaluated by telephone/email follow up at 3, 6 and 12 months post abortion (complete, partial or no expulsion. The exact day of expulsion will be noted to determine the risk of expulsion as a function of time post insertion),

- Continued use of IUC at 3, 6 and 12 months post insertion evaluated by telephone follow-up (continued use/voluntary discontinued use, involuntary discontinued use including expulsions etc) reasons for discontinuation will be recorded and subsequent use of other contraceptive methods will be noted)
- Ease of insertion according to health care provider (judged as very easy, moderately-, or very difficult)
- pain at time of insertion (women will indicate the pain before insertion, at placement of tenaculum, sound and IUC by putting a vertical mark on a 10 cm long horizontal line with a Visual Analogue Scale (VAS) from 0, indicating no pain to 10 indicating worst imaginable pain. Result will be noted in millimeters and entered into case report forms).
- Post-abortion bleeding (number of days of fresh bleeding and spotting after the abortion)
- Reasons for non-attempted insertion of IUC (change of mind, heavy bleeding, not coming for insertion, staff being unavailable etc),
- Complications (adverse events (AE) and serious AE) bleeding requiring any treatment, uterine perforations and cervical tears, infection requiring treatment with antibiotics, hospitalization for any reason, surgical procedures due to heavy bleeding, incomplete abortions, prolonged bleeding or patient request,
- Pregnancies occurring during the 12 month follow-up (planned and unplanned, wanted and unwanted, pregnancy outcomes- ectopic, miscarriage, abortion, molar, kept pregnancy),
- Acceptability of immediate and delayed insertion of IUC by asking women if they would recommend the procedure to a friend (yes/no, asked at the time of insertion and at the 3, 6 and 12 month follow up),
- Acceptability of IUC as post abortion contraception- evaluated as above,
- The proportion of surgical procedures in total and for each study site (type of procedure, reasons therefore- infection, retained products of conception, prolonged bleeding etc).

Follow up for all women will be by telephone (call) and/or email (by special invitation to a link) with a structured questionnaire with multiple choice questions at 3, 6 and 12 months post abortion when primary and secondary objectives will be reported as described above. Women will answer questions regarding: post abortion bleeding and current bleeding pattern, continued use of IUC/other use of contraception, reasons for non-use of IUC (expulsion, never inserted- reasons, extracted- reason for this), complications (expulsion, infection, surgical intervention

etc), satisfaction with their current contraceptive method and experience of unintended/intended pregnancy and the results of these pregnancies. In addition, patient records in both groups will be reviewed after 6 months in order to extract information concerning possible extra visits related to the abortion or IUC related complications.

Data will be recorded on individual printed case report forms (CRFs), after which they will be entered via a digital case report form (eCRF) using a centre-specific module. Data quality will be assured by both computer-generated verification of consistency and by manual review at monitoring visits. E-CRFs from all sites can only be accessed by the PI and will be transferred into a database. The database will contain information on demographic variables, type of IUC inserted and sound measurement in addition to the variables above.

The end of study is defined as completion of the last visit of the last subject. The sponsor and the investigators reserve the rights to discontinue the study at any time for safety reasons or other reasons jeopardizing the justifications of the study.

An interim analysis of results will be performed when 50 percent of women have been recruited in any gestational strata. If expulsion rates exceed 20 percent or if acceptability rates are below 50 percent by the 3 month follow up the study will be stopped. If the study is prematurely terminated or suspended, the investigator should promptly inform the participants and assure appropriate therapy and follow-up.

## **6 Study population**

Women with unwanted pregnancy having a medical abortion and fulfilling inclusion and without exclusion criteria and opting for IUC as post abortion contraception. The medical abortion will be carried out according to the Swedish national evidence based guidelines.

### ***6.1 Inclusion criteria***

- Above 18 years old,
- eligible for medical abortion,

- opting for post abortion IUC,
- able and willing to comply with planned follow up.

## ***6.2 Exclusion criteria***

- Contraindication for medical abortion or
- Contraindication for IUC (contraindications may be present for LNG-IUSs but the woman may still choose a Cu-IUD and thereby enter the study),
- inability to give informed consent.
- Septic abortion
- Known hypersensitivity/allergy to levonorgestrel or any of the substances added to the LNG-IUS
- Known abnormal uterine cavity
- Chorioamnionitis
- Abortion associated bleeding > 1000ml
- Uterine atony postabortion
- Placental retention
- Therapeutic antibiotic treatment during abortion, (antibiotics used only as prophylaxis is accepted)
- History of breast cancer
- If any of the following conditions are present an individual evaluation and decision must be done before inclusion: pelvic or genital infection, cervicitis, immunocompromised women, untreated cervical dysplasia, neoplasia in cervix or uterus, acute liver disease or hepatic neoplasia, migraine or other very severe headache, icterus, high uncontrolled blood pressure, serious arterial disease i.e. stroke or myocardial infarction, acute venous thrombosis

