## ***6.3 Withdrawal criteria***

Patients may be discontinued from the study at any time. Specific reasons for discontinuation can be;

- Every subject is free to drop-out of the study at any time. These subjects will receive contraceptive counseling and treatment according to local routines and will suffer no negative consequences
- Serious adverse events
- Post abortion infection between randomization and planned insertion

Women who discontinue due to side effects or adverse events will be asked permission for follow up for a total of 12 months post abortion.

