## **17 Statistical considerations - Sample size**

### ***17.1 Justification of power calculation***

A total of 720 women will be recruited. In order to be able to show a difference of 80 percent in IUC usage in the immediate insertion group at 6 months post insertion compared to 60 percent use in the delayed group with a power of 90 percent and an alpha of 0.05 we would need to randomize 109 women in each group. If close to 100 percent of women receive the IUC in the immediate group and there is an expulsion rate of maximum 15 percent (immediate post placental insertion after delivery has expulsion rates of 15 percent) and some women have the IUC removed a use of approximately 80 percent could be expected in the immediate group. In the delayed group fewer women are estimated to come for insertion and the expulsion rate is estimated at 5 percent.

We will stratify women in three gestational age categories ( $\leq 9$  weeks+0 days, 9weeks +1 day  $\leq 12$  weeks+0 days, and  $>12$  weeks) to make study data more internationally applicable. We will compensate for surgical procedures due to incomplete abortions and prolonged bleeding which is estimated to be needed in approximately 3-5 percent (13). We will also compensate for a 15 percent loss to follow up which is commonly seen in studies in abortion. Thus, we will randomize 240 women in each gestational strata (total 720 women). Analysis will be presented as intention to treat for all randomized women as well as per protocol for women completing the 6 month follow up (see analysis plan). Follow up at 3, 6 and 12 months will be performed by telephone/email. In women who does not attend FU electronic patient records will be searched for main and secondary outcomes (safety, pregnancy, abortion).

- Primary outcome:

The primary outcome is the difference in women with IUC use at 6 months between the two groups (immediate and delayed insertion). The results will be analyzed by Fisher's exact test. A sensitivity analysis will be performed using logistic regression taking center, parity and age into account.

- Analysis populations

The main analysis population for primary outcome will be a modified intention to treat (mITT). This population is all randomized women, with medical abortion, and follow up for main outcome recorded at 6 months. Hence, also women with no insertion and women experiencing expulsion are included in this mITT.

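### Women are randomised before several exclusion and withdrawal conditions can occur, and the protocol does not say that such women stay in follow-up and in the primary analysis

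*Protocol*

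**What the plan says.** **Timing of randomisation.** Protocol section 5 (Randomization) states: "Randomization will be performed by the midwife in the family planning/ abortion clinic at the time of intake of mifepristone". This follows the eligibility judgement and signed consent. The same section says: "The study will for practical and ethical reasons not be blinded".

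**Exclusion criteria.** Section 6.2 mixes conditions that can be checked at that moment with others that cannot: "Abortion associated bleeding > 1000ml", "Uterine atony postabortion", "Placental retention" and "Therapeutic antibiotic treatment during abortion" (prophylactic use is allowed). Section 6 defines the study population as women who meet the inclusion criteria and have no exclusion criteria.

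**Withdrawal.** Section 6.3 gives, among possible reasons for discontinuation from the study, "Post abortion infection between randomization and planned insertion". Women who stop because of side effects or adverse events are asked for permission to be followed to 12 months.

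**Analysis.** Section 17.1 defines the main (modified ITT) set: "This population is all randomized women, with medical abortion, and follow up for main outcome recorded at 6 months". It adds that women without insertion and women with expulsion are included. A stricter ITT set, with imputation for women lost to follow-up, is a sensitivity analysis. Under Missing data, a woman with no primary outcome is classed as a drop-out.

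**The concern.** A criterion that can only be met after allocation cannot act as an eligibility criterion. It becomes a rule for handling randomised women. Here it operates in an open-label trial, and for infection it operates over a period that depends on the allocated arm. Such events may also make insertion, and hence use at 6 months, less likely. If meeting one of them ends a woman's participation and her 6-month outcome is then not recorded, she leaves the main analysis because of something that happened after randomisation. The two groups are then no longer the groups that were randomised. Women in whom insertion could not go ahead as planned also belong to the trial's question, which is whether offering early insertion leads to more use at 6 months.

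**Working it through.** **1. Order of events.** Mifepristone intake is when the woman is randomised. The abortion follows, and insertion comes within 48 hours of it (immediate arm) or at 2 to 4 weeks (delayed arm), as the Synopsis states under Intervention and Control. Against this order:
- Bleeding above 1000 ml, therapeutic antibiotics during the abortion and placental retention arise in the course of the abortion, after randomisation.
- Uterine atony is post-abortion by its own wording, so it too comes after randomisation.
- Infection in section 6.3 is after randomisation by its own wording.

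The window for infection runs from the abortion to planned insertion: at most 2 days in the immediate arm and 14 to 28 days in the delayed arm. The delayed arm is exposed to this criterion at least 14/2 = 7 times as long.

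**2. Status of a randomised woman who then meets a section 6.2 condition.**
- Section 6: outside the study population.
- Section 5 (Variables and measures): heavy bleeding is a listed reason for non-attempted insertion, so she contributes an outcome.
- Section 6.3: the permission rule covers women stopping for side effects or adverse events. Nothing says whether a woman excluded under 6.2 comes under it.
- Section 17.1: in the main analysis set if her 6-month outcome is recorded, otherwise not.

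Two sites could follow the text and treat the same woman in opposite ways.

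**3. The plan's own figure.** Section 17.1 assumes 80% versus 60%, power 90% and alpha 0.05, and gives 109 per group. With a two-sided test and pooled variance:

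n = [1.960·√(2·0.70·0.30) + 1.2816·√(0.80·0.20 + 0.60·0.40)]² / 0.20² = (1.270 + 0.811)² / 0.04 ≈ 108.2, rounded up to 109.

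The figure reproduces. It does not bear on the timing conflict, but it supplies the rates used below.

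**4. Illustration of possible size (assumed inputs).** Let a share e of one arm be removed, let u be the use rate those women would have had, and let p be the arm's true rate. The observed rate is (p − e·u)/(1 − e). With e = 5%:
- Removed from the immediate arm, u = 0: 0.80/0.95 = 84.2%; difference 84.2 − 60.0 = 24.2 points.
- Removed from the delayed arm, u = 0: 0.60/0.95 = 63.2%; difference 80.0 − 63.2 = 16.8 points.
- Removed from both arms, u = 0: 84.2 − 63.2 = 21.1 points (before rounding, 84.21 − 63.16 = 21.05).
- Removed from the immediate arm, u = 30%: (0.80 − 0.015)/0.95 = 82.6%; difference 22.6 points.
- Removed from either arm with u = p: no change, 20.0 points.

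**5. The same with no true effect (70% in both arms, u = 0, one arm only).**
- e = 3%: 0.70/0.97 − 0.70 = 2.2 points.
- e = 5%: 0.70/0.95 − 0.70 = 3.7 points.
- e = 10%: 0.70/0.90 − 0.70 = 7.8 points.

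Take 360 × 0.85 = 306 women per arm after the protocol's 15% loss, and a normal-approximation two-sided 5% test. For e = 5% the arms hold 290.7 and 306 women. The null standard error is 0.0369 and the unpooled one 0.0368. The rejection probability is Φ((0.0368 − 1.96·0.0369)/0.0368) + Φ((−0.0368 − 1.96·0.0369)/0.0368) ≈ 0.17. For 3% and 10% it is about 0.09 and 0.57.

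**The case against.** The strongest reply is that the protocol never says these women are taken out of the analysis, and that is correct. A reader might infer that sections 6.2 and 6.3 remove women from the comparison, or that the ITT commitment is breached. The text does not support either reading. Section 17.1 names none of these events as a reason to leave a set, keeps women with no insertion, and adds a strict ITT that imputes lost outcomes. Section 6.3 is permissive. Records are searched for women who miss follow-up, and are reviewed in both groups after 6 months. Removal requires two steps: a site treats 6.2 or 6.3 as leaving the study, and no 6-month outcome is then recorded.

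A reader might also infer that bleeding, atony and retention are found more often in the immediate arm because those women are seen sooner. The protocol does not say so. These conditions arise around the abortion in both arms, and adverse events are asked about at every contact (section 12.3). An arm-dependent window is plain only for infection.

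Nor does the text support the inference that the bias must favour immediate insertion. Infection discontinuations have the longer window in the delayed arm, and losing non-users there would shrink the difference.

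What stands is the timing conflict, the unequal infection window, and the lack of any statement that these women remain in follow-up. The safeguards narrow the gap without closing it: permission can be refused, and the main set depends on a recorded outcome.

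**Conclusion.** The conflict between the time of randomisation and sections 6.2 and 6.3 is certain from the text. So is the difference in the infection window: at most 48 hours after the abortion against 2 to 4 weeks. Loss of randomised women from the primary comparison is a possible consequence of applying those sections as written; it is not a stated rule.

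The size and direction of any bias cannot be derived. The protocol gives no rate for these events by arm. Its only related figure is 3 to 5% for surgical procedures, which is not arm-specific and does not describe the same events. The shift from 20 points to about 24 or 17 is therefore an illustration. It assumes 5% removed from a single arm and no users among them. It falls to about 1 point if both arms lose 5%, and to zero if the removed women would have used IUC at the same rate as their arm. The type I error figures rest on the same extreme assumption.

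The point is more than missing detail, because following the stated rules literally can end follow-up of randomised women on the basis of post-allocation events. Outcomes never collected for that reason cannot be recovered at analysis; they can only be imputed.

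**What to change.** Reconcile section 5 (Randomization) and sections 6, 6.2, 6.3 and 17.1:

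1. Split section 6.2 into criteria assessed before randomisation and conditions that may arise after it. State that the study population in section 6 is defined by the first list only.
2. Record the later conditions, and the infection in section 6.3, as reasons for non-attempted or postponed insertion. Section 5 already collects reasons for non-attempted insertion.
3. State that none of these ends the 3-, 6- and 12-month follow-up unless the woman withdraws consent.
4. State in section 17.1 that these women remain in the primary analysis in their allocated group, classified by actual IUC use at 6 months.

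The clinical decision on whether and when to insert is left exactly as it is. The cost is amendment wording, with no extra visits. The one downside is that the observed effect may be somewhat smaller, because women in whom insertion was not possible are counted.
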